⁹⁹Tc-MDP in Postmenopausal Women With Differentiated Thyroid Cancer and
Osteoporosis

Trial registration: NCT02304757

April 16, 2021

Study Protocol

Study Type: Interventional

Study Design: Treatment, Parallel Assignment, Single Blind (Outcomes Assessor), Non-Randomized, Efficacy Study

Patients recruitment

This was an open-label, prospective non-randomized study carried out in three centers (ClinicalTrials.gov ID: NCT02304757) from November 2015 to December 2019. Postmenopausal women are eligible in the study fulfilling all the following criteria. (1) They were pathologically diagnosed with DTC including papillary or follicular carcinoma. (2) They received a near total thyroidectomy and radioiodine treatment. (3) TSH suppression should be at least one year before the study. (4) Bone mineral density (BMD) in lumbar spine and/or hip was tested by Dual-energy X-ray absorptiometry (DXA) at baseline, 6 month (m) and/or 12m follow up. 5) The diagnosis of osteoporosis was T-score ≤ -2.5 SD at the lumbar spine, or hip.

We excluded patients considering the following criteria: (1) patients having medications for OS before TSH suppression treatment; (2) secondary OS; (3) severe liver or kidney disease; (4) myelosuppression; (5) digestive disease; (6) long term use of immunosuppressive agent, estrogen or estrogen receptor modulators. This study was approved by the Institutional Review Board of Hospital Research Ethics. All the patients were fully acquainted with their treatment and consented to participate in the clinical trial.

TSH suppression treatment

TSH suppression treatment was based on the risk stratification of DTC using levothyroxine (L-T₄) as recommended

Treatment protocol for osteopenia and osteoporosis

Patients with OS were divided into ⁹⁹Tc-MDP and alendronate treatment groups.

1. ⁹⁹Tc-MDP treatment group: 15mg ⁹⁹Tc-MDP were intravenously administered twice a week for 10 weeks, then once a week for 8 weeks, every two weeks for 22

weeks and monthly for another 3m.

2. Alendronate treatment group: 70mg alendronate (Merck & Co., Darmstadt, Germany) was administered orally once a week for 12m.

Laboratory assays

Bone alkaline phosphatase (ALP), osteocalcin and propeptide of type I procollagen (PINP), and C-terminal telopeptide of type I collagen (CTX) were all determined by enzyme-linked immunosorbent assay (Modular E170, Hoffmann-La Roche, Basel, Switzerland). Free T₃, free T₄, thyroid stimulating hormone (TSH) was measured using a time-resolved immunofluorometric assay (Anytest, sym-bio lifescience co., ltd, Shanghai, China). 25(OH) D, parathyroid hormone (PTH), serum calcium and phosphorus and other laboratory tests were measured as routine at baseline and 12m.

Analysis of knee relief, QOL and adverse reaction

Lysholm knee (LYS) rating scale was used to evaluate the knee function at baseline and 12m. QOL in patients with OS was measured with a 36-item Short Form Health Status Survey questionnaire (SF-36) at baseline and 12m. SF-36 including four physical and fundamental items were calculated which represent the deviation from the reference population. The higher score by SF-36 and LYS means a better QOL and knee function. A treating physician reviewed the clinical results and any discomfort at each visit.

Statistical Analysis Plan

The predetermined primary end point was the difference in the change in BMD of the lumbar spine between the two groups. Sixty four sample size was assumed to achieve 80% power to detect non-inferiority using a one-sided two sample t-test. The margin of non-inferiority is 0.5% percent. The true difference between the means is assumed to be 0. The significance level (alpha) of the one sided test is 0.025. The data were drawn from population with standard deviations of 0. Consider the 10% loss of

follow-up rate, group sample size was 70 cases.

Continuous data are expressed as the mean \pm standard deviation. Independent sample t-test by SPSS 22 was used to compare the basic information, clinical characteristics within groups at baseline and the difference values of BMD between that at baseline and 6m and 12m after treatment. Differences in BMD, QOL by SF-36 questionnaire, bone turnover marks and other laboratory results were determined using a paired t-test (one-sided tests) and Mann-Whitney U test. A Fisher exact test was used to compare the adverse events. Pearsman Rho was used to analyze the correlation of lumbar uptake of Na^{18}F and BMD/T value by DXA. P value <0.05 was considered statistically significant.

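### Treatment is not randomised and no assignment rule is given, yet lumbar BMD change is compared only by unadjusted tests and nothing follows if the groups differ at baseline

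*Combined protocol and SAP*

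**What the plan says.** Under Patients recruitment the protocol says: "This was an open-label, prospective non-randomized study carried out in three centers". The only description of allocation is under Treatment protocol for osteopenia and osteoporosis: "Patients with OS were divided into ⁹⁹Tc-MDP and alendronate treatment groups". Nothing says who chose the treatment or on what basis.

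The Statistical Analysis Plan sets the endpoint: "The predetermined primary end point was the difference in the change in BMD of the lumbar spine between the two groups". It sizes the study on an unadjusted comparison: "Sixty four sample size was assumed to achieve 80% power to detect non-inferiority using a one-sided two sample t-test", with "The significance level (alpha) of the one sided test is 0.025".

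For the analysis, "Independent sample t-test by SPSS 22 was used to compare the basic information" and clinical characteristics at baseline, and the same test covers "the difference values of BMD between that at baseline and 6m and 12m after treatment". A further sentence says that differences in BMD and other outcomes "were determined using a paired t-test (one-sided tests) and Mann-Whitney U test". The remaining methods are a Fisher exact test for adverse events and a correlation. No regression, matching, stratification, propensity score or centre term is listed, and no step is tied to the baseline comparison.

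**The concern.** A two-sample t-test gives its nominal error rate when the group means differ only through treatment and chance. Randomisation secures that; an unstated choice of treatment does not. Any factor that affects BMD change and is unevenly spread between the groups shifts the estimated difference, and the standard error does not cover the shift.

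The protocol shows one possible route to imbalance: the degree of TSH suppression follows thyroid cancer risk, and nothing keeps that mix equal between groups. Age, 25(OH)D, PTH and centre are further candidates. That these factors affect BMD change is my assumption; the documents do not say so.

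At stake is the non-inferiority claim. A shift favouring ⁹⁹Tc-MDP inflates the chance of a false claim, and a shift against it costs power.

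**Working it through.** **Inputs from the SAP.** Margin 0.5% (read as 0.5 percentage points of BMD change), true difference 0, one-sided alpha 0.025, power 80%, sample size 64.

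**Assumptions.** The 64 is read as per group, because the figure after allowance for loss to follow-up, 70, is stated for a group. The SD prints as 0, which cannot be used and may be an extraction fault, so SD 1 is assumed. Imbalances and correlations are illustrative.

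**Step 1: the plan's own figure.** With n = 64 per group, df = 126 and the critical value is 1.979. The standard error is SD × √(2/64) = 0.1768 at SD 1. The non-centrality for power is 0.5/0.1768 = 2.83, and the non-central t distribution gives power 80.1%. So SD 1 recovers the stated 64.

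**Step 2: how far the baseline t-test can see.** The largest observed imbalance with P ≥ 0.05 is 1.979 × √(2/64) = 0.35 SD. If the population imbalance is 0.35 SD, the test is significant in about half of trials (power 50%).

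**Step 3: effect on the primary test.** Let one covariate differ by 0.35 SD in the population, in the direction favouring ⁹⁹Tc-MDP, and have within-group correlation r with BMD change.

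- Bias = 0.35 × r × SD
- Non-centrality δ = 0.35 × r / √(2/64)
- Type I error at the margin = P(T′ > 1.979), where T′ is non-central t with 126 df and non-centrality δ

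The SD cancels in δ, so these error rates do not depend on SD 1.

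| r | Bias at SD 1 | δ | Type I error, all trials | Among trials with non-significant baseline test | After adjusting for the covariate |
|---|---|---|---|---|---|
| 0.2 | 0.070 | 0.40 | 5.9% | 4.0% | 2.5% |
| 0.3 | 0.105 | 0.59 | 8.5% | 4.9% | 2.5% |
| 0.5 | 0.175 | 0.99 | 16.4% | 6.6% | 2.5% |

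The last two columns are from simulation (200,000 trials per row); the others are closed-form.

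**Step 4: the trials where the imbalance is seen.** Each half carries about half the weight, so the error among trials with a significant baseline test is about 2 × 5.9 − 4.0 = 8%, 2 × 8.5 − 4.9 = 12% and 2 × 16.4 − 6.6 = 26%. The larger share of the excess lies where the imbalance has been detected, and there the plan specifies no action.

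**Step 5: if 64 were the total.** With 32 per group, √(2/32) = 0.25, so δ = 0.28, 0.42 and 0.70. With 62 df the type I error is about 5%, 6% and 10%. The direction of the finding is unchanged.

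**The case against.** Several points on the other side are fair.

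- **Restriction.** All women are postmenopausal, have a T-score at or below −2.5 and have had at least a year of TSH suppression. Secondary osteoporosis, osteoporosis drugs before TSH suppression, and long-term estrogen, receptor-modulator or immunosuppressant use are excluded. This narrows some confounders but does not make the groups alike on what remains.
- **Blinded outcome assessment.** It protects measurement, not selection into groups.
- **Change scores.** They remove additive baseline BMD differences, but not factors that alter the rate of change.
- **No documented magnitude.** The SD, imbalance and correlations above are all assumed. This stands, and it limits what can be said about size.
- **Post hoc choice.** Recruitment ended in December 2019 and the document is dated April 2021, so covariates would be chosen after data collection. This also stands and has to be disclosed.

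A reader might go further and infer that undetected imbalance could lift the error rate to around 20%. A bias of 0.2 points at SD 1 does give 20.1%. But one covariate needs an imbalance of 0.2/r to produce it: 1.0, 0.67 or 0.40 SD at r = 0.2, 0.3 or 0.5. The planned baseline test would flag those with power of over 99%, 96% and 61%. A bias of that size would need a strong covariate, several acting together, or unmeasured factors, and adjustment cannot remove the last of these. The documents give no basis for assuming any of them.

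**Conclusion.** The concern holds for the absence of any adjustment. Allocation is non-randomised with no stated rule, every test of lumbar BMD change is unadjusted, and the baseline comparison leads to no action. The 2.5% error rate is therefore conditional on selection causing no bias.

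Under the illustration (64 per group, one measured covariate 0.35 SD apart in the population), type I error is about 6%, 9% or 16% overall. It is about 4%, 5% or 7% where the baseline test is non-significant, for correlations of 0.2, 0.3 and 0.5. These are not estimates for this trial. The documents do not support a statement that the result is biased, or that any bias favours ⁹⁹Tc-MDP. The point should be fixed because the remedy is cheap and bears directly on the primary claim.

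**What to change.** Base the non-inferiority confidence interval on one named covariate-adjusted difference in lumbar BMD change. Use values already collected: age, 25(OH)D, PTH and centre, plus TSH if it was recorded at baseline. The protocol documents 25(OH)D and PTH at baseline but does not state when TSH was measured. It does not list age by name; I take it to be part of the baseline information.

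Alongside it:

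- Keep the unadjusted t-test as a sensitivity analysis.
- Show one further model that adds baseline lumbar BMD, because ANCOVA and change-score results can differ in non-randomised groups.
- Tabulate treatment by centre. If the two coincide, omit the centre term and say that their effects cannot be separated.
- Report standardised baseline differences.
- Describe how treatment was assigned.
- Label the adjustment as added after data collection, and word the conclusion as subject to residual confounding.

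Do not add a rule that any disagreement between analyses voids the claim. With no bias at SD 1, three such analyses disagree by chance in about 6% to 13% of trials.

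The cost is analysis time and some model dependence. Degrees of freedom cost little: at SD 1, power is about 78% instead of 80% if seven covariate terms explain nothing. Overlap between treatment and covariates costs more: if covariates explain 30% or 50% of treatment assignment and bring no gain in precision, power at SD 1 falls to about 65% or 51%. Women with a missing covariate would drop out of a complete-case fit, so the number analysed should be stated.

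### The primary comparison pools three centres in an unadjusted t-test, although allocation was neither randomised nor balanced by centre and the margin is only 0.5%

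*Combined protocol and SAP*

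**What the plan says.** **Design.** The protocol's Patients recruitment section describes an "open-label, prospective non-randomized study carried out in three centers", running "from November 2015 to December 2019". On allocation, the treatment section says only "Patients with OS were divided into" the two treatment groups. It gives no method, ratio, stratification or balancing by centre.

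**Measurement.** Inclusion criterion 4 says that lumbar spine and/or hip BMD "was tested by Dual-energy X-ray absorptiometry (DXA) at baseline, 6 month (m) and/or 12m follow up". The documents name the platforms for the bone-marker and thyroid assays but no DXA device. They do not mention a same-scanner rule, phantom checks, drift correction, cross-calibration or central reading.

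**Analysis.** The SAP states: "The predetermined primary end point was the difference in the change in BMD of the lumbar spine between the two groups". It also states: "The margin of non-inferiority is 0.5% percent". The sample-size statement reads "Sixty four sample size was assumed to achieve 80% power to detect non-inferiority using a one-sided two sample t-test", with one-sided alpha 0.025, a true difference of 0 and an SD printed as 0. BMD differences from baseline to 6m and 12m are compared between groups by an independent-sample t-test. No centre, scanner or calendar-time term appears.

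**The concern.** Three features act together. The margin is small. Non-random allocation leaves one centre free to hold much more of one group than of the other. The planned test treats all women as one sample, so it cannot separate a centre effect on measured change from a treatment effect.

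The endpoint is a within-woman change, so what matters is anything that moves the change at one centre relative to the others. Examples are drift, a recalibration or a scanner replacement between a woman's scans, or care that differs by centre and affects bone. Adjusting for baseline characteristics would not remove an error that arises between the two scans, and blinding the outcome assessor does not address it.

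At stake is the validity of the non-inferiority conclusion in either direction. A shift favouring the test group can hide a loss as large as the margin. A shift against it can make an equivalent treatment fail.

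**Working it through.** **Inputs from the documents:** three centres; margin 0.5, read here as percentage points of BMD change; one-sided alpha 0.025; true difference 0; n = 64, not stated as per group or total.

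**Assumed, because the documents do not give them:** SD, size of the shift, centre shares, and the fraction of women affected.

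**1. The plan's own figure.** With the printed SD of 0 the formula returns n = 0, so 64 cannot be reproduced as written. It is reproduced with SD 1.0 and 64 per group (t-test power 80.1%), or with SD 0.7 and 64 in total. The two readings give nearly the same standard error:
- SE = 1.0 × √(2/64) = 0.177
- SE = 0.7 × √(2/32) = 0.175

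I use SD 1.0 with 64 per group, and SD 3.0 (SE = 3.0 × √(2/64) = 0.530) to show the range.

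**2. Bias.** For a shift at one centre:

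bias = shift × (difference in centre share) × (fraction of that centre's women affected)

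- Every woman affected: 1% × (0.60 − 0.30) × 1 = 0.30
- One third affected: 1% × (0.60 − 0.30) × 1/3 = 0.10

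One third is close to what a single step on one date would produce. The study period spans about 50 months. With even enrolment over about 38 months and 12 months of follow-up (assumed), at most 12/38 = 32% of women have a baseline-to-12m interval that spans any one date. The bias is then 0.30 × 0.32 ≈ 0.095.

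**3. False non-inferiority** when the true difference equals the margin and the bias favours the test group: P(Z > 1.96 − bias/SE).

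| Bias | SD 1.0 | SD 3.0 |
|---|---|---|
| 0 | 2.5% | 2.5% |
| 0.10 | 8.2% | 3.8% |
| 0.30 | 39.6% | 8.2% |

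The exact t-test gives 8.1% and 39.1% at SD 1.0, and 3.8% and 8.1% at SD 3.0. The single-step bias of 0.095 gives 7.7% and 3.7%.

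**4. Power** (exact t-test) when the true difference is 0 and the bias runs against the test group.

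| Bias | SD 1.0 | SD 3.0 |
|---|---|---|
| 0 | 80% | 15% |
| 0.10 | 61% | 11% |
| 0.30 | 20% | 6% |

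**5. Cost of a centre term.** Assume equal groups, the 60/30 split, and the remaining women divided between the other two centres in the same proportions in both groups. The squared correlation of treatment with centre is (0.25 × 0.30)² / (0.25 × 0.45 × 0.55) = 0.0909. The variance inflation is 1/(1 − 0.0909) = 1.10, so the standard error rises by √1.10 = 1.049, about 5%. At SD 1.0 the SE goes from 0.177 to 0.185, and power by the normal approximation from 80.7% to P(Z > 1.96 − 0.5/0.185), about 77%.

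**The case against.** The strongest reply is that the documents show no scanner change, no shift and no centre imbalance. The 1% shift and the 60/30 split are assumptions, and the size of the problem cannot be established from the text. That stands. It is why the figures are given as a range, whose lower end (4% against a nominal 2.5%) is modest.

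A reader might infer that scanner differences between the three centres can by themselves decide the result. The documents do not support that. The endpoint is a change within each woman, so a constant offset between machines drops out if she stays on one machine.

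A reader might also infer that the plan lets women be scanned on different machines. Criterion 4 is an eligibility sentence, not an imaging procedure. Its silence shows neither that switching was allowed nor that it occurred.

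Nor does every disturbance bias the comparison. If scanner changes fall equally on both groups, the result is extra noise rather than false non-inferiority. For example, if 20% of women carry a random shift with SD 2%, SD 1.0 becomes √(1 + 0.2 × 4) = 1.34 and power falls to 55%.

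Finally, the period given ends in December 2019 and the document is dated April 2021, so new scanning rules cannot change scans already taken.

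What survives is the analysis. Allocation leaves centre imbalance uncontrolled, and the stated test does nothing about it.

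**Conclusion.** The concern holds as a weakness of the primary analysis. An unadjusted pooled t-test leaves the group difference open to any centre-level shift in measured BMD change, in proportion to the imbalance in centre shares, and the margin is small enough for a modest shift to matter.

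Under a 1% shift and a 60/30 split, false non-inferiority at the margin is about 8–40% if the SD is 1.0 with 64 per group, and 4–8% if it is 3.0. The upper ends need every woman at that centre to be affected; the lower ends correspond to about one third.

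Confidence in the missing centre term is high. Confidence in the size is low, because it rests on assumed shift, split and SD. The SD printed as 0 and the unclear meaning of 64 are separate defects, and correcting them would not resolve this one.

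**What to change.** 1. In the SAP, replace the t-test for the primary endpoint with a linear model of lumbar spine BMD change on treatment and centre. Judge the adjusted difference and its 95% confidence interval against the margin.
2. Tabulate women by centre and group before fitting. A centre that supplied only one group contributes nothing to the adjusted comparison, and the report should say so.
3. Add a sensitivity analysis limited to women whose baseline and follow-up scans were on the same scanner, and tabulate any scanner changes by group. If no machine changed, one sentence saying so is enough.
4. As the document postdates the study period, date the change, say whether outcome data had been seen, and report the unadjusted result beside the adjusted one.

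**Cost.** SAP wording, one model, and retrieval of the scanner identity for each scan, if those records exist. The interval widens somewhat when centre and treatment are correlated: about 5% in standard error for a 60/30 split, and more if the alignment is stronger.

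**What it leaves open.** The centre term removes a shift shared by a centre's women. It cannot be relied on for a mid-study step that touches only some of them, because the two groups there may have been scanned at different times. The same-scanner analysis addresses machine switches and replacements, but it does not catch a recalibration of a single machine.

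### Criterion 4, read literally, ties eligibility to a follow-up DXA and accepts hip-only scans; no analysis set or missing-scan rule settles who is counted

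*Combined protocol and SAP*

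**What the plan says.** The Patients recruitment section opens its inclusion list with "Postmenopausal women are eligible in the study fulfilling all the following criteria", so each numbered item is a condition of entry.

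- Criterion 3 looks backwards: "TSH suppression should be at least one year before the study".
- Criterion 4 names both scan site and timing: "Bone mineral density (BMD) in lumbar spine and/or hip" and "was tested by Dual-energy X-ray absorptiometry (DXA) at baseline, 6 month (m) and/or 12m follow up".
- Criterion 5 takes the osteoporosis diagnosis from a T-score of -2.5 or lower, "SD at the lumbar spine, or hip".

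The Statistical Analysis Plan section sets a lumbar endpoint: "The predetermined primary end point was the difference in the change in BMD of the lumbar spine between the two groups". On size it says "Sixty four sample size was assumed to achieve 80% power to detect non-inferiority", then allows for 10% loss and arrives at a group size of 70. It lists t-tests for baseline characteristics and for BMD change to 6 and 12 months, and a Fisher test for adverse events. It names no population for any of these and no rule for a missing DXA. The study ran "from November 2015 to December 2019"; the document is dated April 2021.

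**The concern.** Whether a woman has a 6- or 12-month scan is known only months after treatment starts. If that decides eligibility, a woman who starts treatment and is never rescanned is classed as ineligible rather than missing. An entry rule governs every analysis, so she would leave three tallies that need no follow-up scan: loss to follow-up, the baseline comparison and the adverse-event comparison. A woman who stopped early because of an adverse event is the obvious example. Allocation was not randomised, so the baseline comparison is the plan's main evidence that the groups are alike; it would then describe only the women who stayed.

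Two related gaps do not depend on how criterion 4 is read. No criterion requires the lumbar scan that the primary endpoint needs. And with no analysis set or missing-scan rule, the lumbar t-test uses only women who happen to have the scans.

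**Working it through.** **1. The plan's own figures.** The inputs from the Statistical Analysis Plan section are margin 0.5, true difference 0, one-sided alpha 0.025 and power 80%. The standard deviation is printed as 0, which cannot be used and may be a lost digit, so 64 cannot be reproduced directly. Power is P(T > t(0.975, 2n-2)), where T is noncentral t with 2n-2 degrees of freedom and noncentrality 0.5 / (SD × √(2/n)).
- With 64 per group, SD = 1.00 gives 80.1%.
- If 64 were the total (32 per group), SD = 0.70 gives 80.3%.
- For the loss allowance, 64 × 1.1 = 70.4 and 64/0.9 = 71.1, so 70 is close to either.

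Below, 64 and 70 are taken as per group and SD as 1.00. Both are assumptions.

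**2. Three readings of criterion 4.**

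| Reading | In favour | Starter with no follow-up scan |
|---|---|---|
| Baseline plus at least one follow-up scan is an entry condition | Placed in a list that must be met in full; names follow-up visits | Ineligible, leaves every analysis |
| Baseline scan alone is enough | The and/or wording permits it | Eligible, missing, no rule for her |
| Misplaced visit schedule | 10% loss allowance; study described as prospective | Eligible, missing, no rule for her |

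**3. Denominators.** At the plan's loss rate, 70 × 0.10 = 7 women per group are unscanned. Counted as missing, loss is 7/70 = 10%. Counted as ineligible, it is 0/63 = 0%. If recruitment ran on to 70 eligible women, 70/0.90 = 77.8, so about 78 per group would have started and about 8 per group would not appear.

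**4. Adverse events (event counts assumed).** Start from 12/70 v 3/70, two-sided Fisher p = 0.026.

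| Women removed | Table | p |
|---|---|---|
| 7 from each group, 1 event in each | 11/63 v 2/63 | 0.016 |
| 7 from each group, 3 events in the first, none in the second | 9/63 v 3/63 | 0.13 |
| 7 from the first group only, 3 events | 9/63 v 3/70 | 0.067 |
| 7 from the second group only, 1 event | 12/70 v 2/63 | 0.010 |

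A proportionate share of events among 7 women in the first group would be 7 × 12/70 = 1.2. The result crosses 0.05 only where events are concentrated among the unscanned.

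**5. Lumbar t-test on scanned women only.** This follows from the missing rule, whatever criterion 4 means. Bias in SD units = (fraction unscanned on ⁹⁹Tc-MDP minus fraction unscanned on alendronate) × gap, where the gap is how much worse unscanned women do, assumed equal in both groups. The one-sided error at the margin, with 64 scanned per group, is:

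| Unscanned, ⁹⁹Tc-MDP v alendronate | Gap 0.5 SD | Gap 1 SD |
|---|---|---|
| Equal | 2.5% | 2.5% |
| 12% v 8% | 3.2% | 4.1% |
| 8% v 12% | 1.9% | 1.4% |
| 10% v 0% | 4.7% | 8.1% |
| 0% v 10% | 1.3% | 0.6% |

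**6. Hip-only women (rates assumed).** If 5%, 10% or 20% of 64 lack a lumbar scan, 61, 58 or 51 per group remain and power is 78%, 76% or 71%.

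**The case against.** The strongest reply is that criterion 4 is simply a visit schedule in the wrong place. An allowance for loss to follow-up has little purpose if women without follow-up scans were never eligible. The study is called prospective and its patients consented; a future scan cannot be checked at entry. The list is loosely drafted: tenses are mixed, and criterion 5 reads as a definition. Discomfort was reviewed by a treating physician at each visit, so collection of adverse events was not tied to DXA. The lumbar endpoint suggests that a lumbar scan was intended. The illustrations rest on event counts, loss rates and an SD that the documents do not give.

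Much of this stands. A reader might infer that women were in fact selected on having follow-up scans, or that the comparison is tilted towards ⁹⁹Tc-MDP. The documents support neither: no exclusion is recorded, at least two other readings are open, and the direction depends on which group lost whom.

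What the reply does not supply is a rule. Expecting 10% loss does not say how those women are counted, and collecting adverse events at visits does not fix the denominator of the Fisher test. Under the schedule reading, the analysis set, the missing-scan rule and the lumbar requirement are still absent.

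**Conclusion.** The point holds as a defect of wording with an unresolved consequence, and should be fixed; confidence is moderate. Followed literally, criterion 4 selects on information obtained after treatment starts, and criteria 4 and 5 admit women without the scan that the primary endpoint needs. Whether the rule was applied that way cannot be told from the documents, and without per-group counts of starters and unscanned women a reader cannot find out.

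The only size that rests on the plan's own numbers is the denominator: 7 of 70 per group at 10% loss, shown as 10% or as 0%. The remaining figures show that conclusions could move in either direction, or not at all if losses and gaps are equal in the two groups. They are not estimates of what happened here. They rest on assumed event counts, loss rates and gaps, on 64 being per group, and on an SD back-solved from an unusable printed value.

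**What to change.** 1. State whether criterion 4 was an entry condition or a visit schedule, and disclose any woman who started treatment and was excluded for lacking a follow-up scan.
2. Define eligibility on baseline information only and list the 6- and 12-month DXA as scheduled assessments. The study is over, so if selection on follow-up scans or entry on hip DXA alone did occur, report it; do not reword it away.
3. Report baseline characteristics and adverse events for all women who started either treatment. Give per group the number of starters, the number with hip DXA only, and the number missing lumbar DXA at 6 months, at 12 months and at both.
4. Define the primary set as all starters with a baseline lumbar DXA, and name the primary method for missing lumbar scans. One option is a likelihood-based repeated-measures model using both follow-up scans, which also keeps women with only one of them. Women with neither scan add little to the estimated change, so add a sensitivity analysis in which unscanned ⁹⁹Tc-MDP women are assumed to do worse.
5. Declare these choices as made after the study ended.

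The cost is a clarifying statement, some SAP text and retrieval of the starter list at three centres. The downside is more missing data to handle and possibly a less favourable estimate.

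### Non-inferiority is tested against a weekly oral comparator with no adherence measure, defined analysis set or assay-sensitivity rule, so under-taken alendronate could hide a moderate true deficit of 99Tc-MDP

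*Combined protocol and SAP*

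**What the plan says.** Under the treatment protocol for osteopenia and osteoporosis, the comparator is "70mg alendronate (Merck & Co., Darmstadt, Germany) was administered orally once a week for 12m". The test drug is given in clinic-type dosing: doses "were intravenously administered twice a week for 10 weeks, then once a week for 8 weeks", then every two weeks for 22 weeks and monthly for 3 months. The recruitment section describes the design: "This was an open-label, prospective non-randomized study carried out in three centers".

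The Statistical Analysis Plan names the primary endpoint: "The predetermined primary end point was the difference in the change in BMD of the lumbar spine between the two groups". It then states: "Sixty four sample size was assumed to achieve 80% power to detect non-inferiority using a one-sided two sample t-test", followed by "The margin of non-inferiority is 0.5% percent". The assumed true difference is 0 and the one-sided alpha is 0.025. A 10% allowance is made for loss to follow-up.

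The only monitoring described at visits is a physician's review of clinical results and discomfort. Bone ALP, osteocalcin, PINP and CTX are measured. The SAP plans one-sided paired t-tests that include BMD and turnover markers.

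The document does not mention a tablet count, diary, dispensing record or minimum intake. It defines neither an all-treated nor a per-protocol set, and has no untreated group. It states neither an expected alendronate effect nor a reason for the margin.

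**The concern.** In a superiority trial, poor adherence usually works against a positive claim. In a non-inferiority trial it can work for one, because a comparator that is not taken is easier to match. Here the two exposures are not equally visible. An intravenous dose on a fixed schedule is either given or missed in front of staff, whereas a weekly oral drug with no supervision described leaves no trace in this plan. The 10% loss-to-follow-up allowance covers women without a BMD result. It does not cover women who return for DXA but have stopped their tablets.

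At stake is what a positive primary result means. It could show that 99Tc-MDP performs within the margin of alendronate as intended to be taken. It could also show that it performs within the margin of alendronate as partly taken, while being worse than the full regimen by more than the margin.

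**Working it through.** **Inputs from the plan.** Margin 0.5, read as percentage points of BMD change; 64 women, read as per group because the inflated figure of 70 is called a group size; one-sided alpha 0.025; power 80%; true difference 0.

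**Assumed inputs (not in the documents).** E is the 12-month lumbar effect of fully taken alendronate over no treatment, 3 to 5 points, with 2 to 6 as a wider range. D is the true deficit of 99Tc-MDP against fully taken alendronate. a is the share of E retained, so 1 − a is the non-taking fraction.

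**The plan's own figure.** The printed SD is 0, which gives n = 0, so 64 does not follow from the printed inputs. With SD 1.0 point, n = 2 × (1.960 + 0.842)² × 1.0² / 0.5² = 62.8, or 63 per group; the exact t calculation gives 64. I therefore use SD 1.0, with 3.0 as a less favourable alternative. (If 64 were the total, the implied SD would be 0.70.)

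**Planned doses.** 99Tc-MDP: 2 × 10 + 8 + 22/2 + 3 = 42. Alendronate: about 52.

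**Shift in the comparator.** Observed deficit = D − (1 − a) × E. The non-taking that shifts the comparator by the full margin is 0.5/E:

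- E = 2: 25%
- E = 3: 16.7%
- E = 5: 10%
- E = 6: 8.3%

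**Chance of declaring non-inferiority when 99Tc-MDP is truly worse** (64 per group, noncentral t, no exposure loss in the 99Tc-MDP group):

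| True deficit D | SD | Non-taking | E = 3 | E = 4 | E = 5 | E = 6 |
|---|---|---|---|---|---|---|
| 0.5 (on the margin) | 1.0 | 0% | 2.5% | 2.5% | 2.5% | 2.5% |
| 0.5 | 1.0 | 10% | 39% | 61% | 80% | 92% |
| 1.0 (twice the margin) | 1.0 | 0% | <0.1% | <0.1% | <0.1% | <0.1% |
| 1.0 | 1.0 | 20% | 8% | 39% | 80% | 98% |
| 1.0 | 3.0 | 0% | 0.2% | 0.2% | 0.2% | 0.2% |
| 1.0 | 3.0 | 20% | 4% | 8% | 15% | 26% |

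**An inactive test drug.** Here D = E, so the observed deficit is a × E. It falls to 0.5 only when a ≤ 0.5/E: 16.7% at E = 3 and 8.3% at E = 6. That is 83% to 92% non-taking, and at that point the chance of passing is still only 2.5%. With E = 5 and SD 1.0, 80% non-taking leaves a deficit of 0.2 × 5 = 1.0 and a chance below 0.1%.

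**Loss in the 99Tc-MDP group.** If that group loses a fraction m of its own effect E − D, the observed deficit rises by m × (E − D). With E = 5, D = 1 and 20% lost in both groups, alendronate shows 4.0, 99Tc-MDP shows 0.8 × 4 = 3.2, and the deficit is 0.8, still outside the margin. A 25% loss in the 99Tc-MDP group alone costs 0.25 × 4 = 1.0, which cancels the shift from 20% non-taking. The bias depends mainly on the difference in exposure between groups.

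**The case against.** The strongest reply has five parts.

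- **Reach of the bias.** A reader might infer that poor tablet-taking alone could carry a worthless drug to success. The documents do not support that: the arithmetic above needs near-total non-taking. This part stands in full.
- **Existing checks.** A reader might also infer that nothing in the plan would show whether alendronate worked. That is too strong. The planned paired tests of BMD and turnover markers would expose gross failure of the comparator. What is missing is a rule saying what follows if they do.
- **Weakness of a simple check.** Requiring only some fall in CTX and some rise in BMD would not catch the non-taking at issue. With E = 5, no untreated change and SD 3 (all assumed), 50% non-taking still leaves a mean gain of 2.5 against a standard error of 3/√64 = 0.375, a ratio of 6.7. This stands, and the fix must carry a quantitative criterion.
- **Weakness of a per-protocol set.** Dispensing is not ingestion, the documents mention no dispensing records, and in a non-randomized study choosing adherers adds selection. This stands as a limit on the remedy, but does not justify leaving analysis sets undefined.
- **Unknown direction and size.** The plan does not say that tablets were unsupervised; that is inferred from a weekly oral drug with no supervision described. With 42 planned infusions, exposure may also be lost in the 99Tc-MDP group, which would push the other way. So the bias is a risk of unknown size, not a demonstrated effect.

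**Conclusion.** The concern holds in a bounded form. The plan has no adherence measure, no defined analysis set and no link from the alendronate group's own response to the non-inferiority conclusion. If exposure is lost more with alendronate than with 99Tc-MDP, the primary result moves towards success.

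For an assumed alendronate effect of 3% to 5%, 17% to 10% non-taking shifts the comparator by the full margin, so the true deficit that can sit at the margin rises from 0.5 to 1.0 point. Under SD 1.0 and E = 5, a deficit of twice the margin goes from below 0.1% to an 80% chance of passing with 20% non-taking; under SD 3.0 it goes from 0.2% to 15%. These sizes rest on assumed E, D, SD and adherence, and on full exposure in the 99Tc-MDP group.

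The documents do not support the inference that an inactive drug would pass, or that the plan contains no information on whether alendronate worked. The point should be addressed because it affects how the primary conclusion is read.

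**What to change.** **1. Exposure and analysis sets.** Report exposure by group from whatever infusion and prescription or dispensing records exist. Define the all-treated set, and a per-protocol set using the same exposure fraction in both groups (for example, at least 80% of planned infusions or of tablets dispensed). Run the primary comparison in both sets. Adjust for baseline variables such as lumbar BMD, TSH, 25(OH)D and center, because neither assignment nor adherence is randomized. Claim non-inferiority only if the lower confidence limit for 99Tc-MDP minus alendronate lies above −0.5 in both sets. If no exposure records exist, say so as a limit on the claim.

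**2. Assay sensitivity.** State the alendronate effect that justifies the 0.5% margin. Compare the confidence interval for the alendronate group's 12-month lumbar gain with it, against a stated numerical threshold. Use the CTX change as support where it was measured; its visit times are not clearly given. If the criterion is not met, call the non-inferiority result inconclusive. This detects gross comparator failure only. Non-taking of 10% to 20% lowers the mean by 0.3 to 1.0 point for E = 3 to 5. Without an untreated group, and with E uncertain by 2 points across that range, such a shortfall cannot be attributed to non-taking.

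**Cost.** SAP wording, one further analysis, and a search for exposure records that may not survive. Per-protocol intervals will be wider, adherers may be a selected group, and the claim becomes harder to reach. The study period ended in December 2019 and the document is dated April 2021, so if results have already been seen, both analyses must be labelled post hoc.
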